Purpose and Objectives

The primary objective of this study will be to evaluate the ability for 2 different ureteral access sheaths to obtain and maintain access to the upper collecting system, as well as evaluate ureteral injury using standardized 5-point classification system.

Secondary endpoints will include evaluating ease of instrument passage, stone extraction, device placement, and radiopacity.

Hypothesis

We hypothesize that the modified designs of Re-Trace and Parallel devices will demonstrate similar safety profiles.

Research method

The proposed study is a prospective randomized controlled trial comparing the safety and efficacy of ureteral access sheaths used in flexible ureteroscopy.

Patients scheduled for flexible ureteroscopy will be identified by the investigator at clinic visits or hospital admission at Cleveland Clinic. The research coordinator will approach patients to determine the patient's initial interest in research, and if interested, the consent process will be initiated prior to surgery.

In order to be eligible the patient must be a suitable operative candidate for flexible ureteroscopy and have an abdominopelvic computed tomography (CT) to delineate pre-operative stone size, with measurements captured in greatest axial and coronal dimensions. Patients who have had prior ipsilateral upper urinary tract reconstructive procedures, ureteral stricture, ureteral malignancy, or impacted ureteral stones will be excluded. Pregnant subjects will also be excluded.

Ureteroscopic treatment of renal calculi is a standard of care treatment approach, and participating in this study will not deviate from standard of care ureteroscopy procedures, however, procedures specific to the research will involve being randomized to the use of one of two ureteral access sheaths:

1. Coloplast Re-Trace
2. Cook Flexor Parallel

Choice of sheath length will be left to the discretion of the surgeon based on body habitus and site of pathology, while sheath diameter will be standardized to 12/14F. Smaller diameter sheaths (11/13F, 10/12F) will be used if significant resistance occurs during advancement, otherwise patients will be excluded from the study if unable to gain ureteral access, or if ureteral balloon dilation or semi-rigid ureteroscopy is required to gain ureteral access.

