If unable to obtain access with the initial sheath the patient is randomized to, the patient will be randomized to a backup sheath. If unable to obtain access with backup sheath, then a second backup sheath will be used. If unable to obtain access with any of the three sheaths with diameter 12/14F, an attempt will be made with up to three additional sheaths of a similar smaller diameter (11/13F or 10/12F), in a random order. If access has not been obtained after randomization to 6 sheaths, the patient will be considered a failure and it will be the surgeon's discretion to either place a stent and do a staged second look at a later time, proceed with ureteroscopy without a sheath, or balloon dilate.

Pre-operative data collection will include age, race, gender, ASA (American Society of Anesthesiologists) score (for comorbidity assessment), body mass index (BMI), and disease history, including stone disease, prior ureteroscopic procedures, vascular disease, and pelvic radiation. Disease fields that will be obtained include stone size (maximal axial and coronal dimensions), degree of hydronephrosis (mild/moderate/severe), and duration of prior ureteral stenting (if applicable).

Intra-operative data will include recording any buckling, kinking, or difficulty in instrument passage that occurs. Surgeons will be asked to subjectively rate the ease of sheath placement, stone extraction through sheath (if applicable), and ease of instrument passage on a scale 1 to 4, with 1 being poor and 4 being excellent. Ureteroscopic video will be taken for all procedures, and ureteral wall injuries will be evaluated after removal of the UAS by a urologist ([name]) blinded to the treatment device using the classification methodology previously described by Traxer and Thomas [3].

UAS related injuries determined by ureteroscopic video will be categorized into five (or 4 per PULS) grades, ranging from 0-4, defined by the following characteristics:

- Grade 0: No ureteral lesion or only mucosal petechiae
- Grade 1: Mucosal erosion or a mucosal flap without smooth muscle injury
- Grade 2: Damage to the mucosa and smooth muscle but no adventitia, with no retroperitoneal tissue visible
- Grade 3: Injury indicating ureteral perforation involving the full thickness of the ureteral wall, including the adventitia
- Grade 4: Total ureteral avulsion

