Location of the primary injury site(s) (lumbar, iliac, pelvic ureter) will also be noted to determine impact on development of future pathology including stenosis, fistula or ureteral stone formation.

Perioperative fields will include OR (surgical) time, type of anesthesia, laser fiber size, guidewire specifications, need for dual lumen catheter or introducer catheter, settings of lithotripsy (if applicable - rate/energy), use of active extraction for fragments (include basket/grasper specifications), any device breakage or damage, and intraoperative complications.

All other procedures associated with standard of care for ureteroscopic treatment of stones, including stent placement, will be left to the discretion of the investigator. Postoperative fields will include postoperative complications, need for ancillary procedures, development or persistence of hydronephrosis/obstruction, and stone-free status at 4 to 6 week postoperative imaging as determined by ultrasound of kidneys, ureters and bladder.

Sample Size

A recent prospective study evaluating ureteral damage in 359 patients undergoing ureteroscopy with a 12/14F diameter sheath found that when using the same 5-point ureteral damage classification system, low grade ureteral injury (score of 0-1) occurred in 86.6% (311/359) of patients, and high grade (score of 2-4) occurred in 13.3% (48/359) of patients.

Based on this preliminary data, the study is powered to detect whether there is a difference between device designs to cause low (0-1) vs. high grade (2-4) ureteral injury. Using an alpha of 0.05 and beta of 0.80, and assuming a difference greater than 20% between groups is considered significant, approximately 49 patients will be required per arm, for a total of approximately 98 patients.

We are requesting the IRB allow for a total enrollment of 117 patients to account for screen failures (inability to gain access, rigid ureteroscopy required, strictures, etc).

Recruitment and Consent

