Based on current volumes of ureteroscopic procedures, we anticipate approximately 2-3 patients per week will be randomized requiring a total of approximately 9-12 months of active enrollment between to reach a total of 100 randomized subjects. Patients will be recruited from either office visits or inpatient hospitalizations. The study coordinator will consent patients using the uploaded consent form accompanying this document. All procedures, devices and protocols are standard of care. There is no additional cost to the patient outside of standard care. The patient's insurance company will be billed for medical costs.

Data Analysis Plan

Data analysis will involve comparisons of ureteral damage between groups related to device design, gender, age, BMI, preoperative stenting, prior stone disease, and prior stone procedures. Differences in operative time, ease of placement, ability to maintain access, and ease of instrument passage will also be evaluated between devices, as well as post-operative complications, success rates, and device failure rates. The analysis will be completed by the approved researchers in coordination with a CCF biostatistician [name]. Study data will be stored on the RedCap database. Data may also be stored on encrypted CCF issued IronKey and encrypted CCF issued computers. Signed consent forms will be stored in a compartment with a lock for the duration of the trial. Approved researchers on this IRB will have access to these data.

Adverse Events and Data Monitoring Committee

The investigator will report any adverse events to the IRB within 10 days of awareness. A data monitoring committee will not be used. The primary risk to participants will be the loss of confidentiality, which will

be maintained by physical and electronic locks. Any unexpected findings of concern will be communicated face-to-face to the patient by the investigator in a clinic visit. A Data Monitoring Committee will not be used for this study as the devices and procedures used are standard care.

Study Costs

REFERENCES

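### The protocol excludes patients in whom access fails but also counts them as failures, so the access part of the primary objective has no settled denominator and no rule for rescue by another device

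*Combined protocol and SAP*

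**What the plan says.** Purpose and Objectives puts obtaining and keeping access into the primary objective, next to graded ureteral injury. The protocol then treats a patient without access in three places.

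- **Research method, sheath-diameter paragraph.** Diameter is standardised to 12/14F, with smaller sizes allowed on significant resistance. The sentence continues: "otherwise patients will be excluded from the study if unable to gain ureteral access". Its last clause adds a second ground for exclusion: "or if ureteral balloon dilation or semi-rigid ureteroscopy is required to gain ureteral access".
- **Research method, backup-sheath paragraph.** "If unable to obtain access with the initial sheath the patient is randomized to, the patient will be randomized to a backup sheath". A second backup follows. The next step is: "If unable to obtain access with any of the three sheaths with diameter 12/14F, an attempt will be made". That attempt may use as many as three smaller sheaths, taken in random order. At the end of this sequence: "If access has not been obtained after randomization to 6 sheaths, the patient will be considered a failure". The surgeon may then stent and stage, "proceed with ureteroscopy without a sheath, or balloon dilate".
- **Sample Size.** About 98 patients are needed (49 per arm), and the request is for a "total enrollment of 117 patients to account for screen failures (inability to gain access, rigid ureteroscopy required, strictures, etc".

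Recruitment and Consent plans enrolment "to reach a total of 100 randomized subjects". The Data Analysis Plan lists success and device failure rates among the comparisons. It defines neither, names no analysis population, and does not say how to score a patient whose assigned sheath fails and who is rescued by another. Research method names two devices, but the backup sequence uses three 12/14F sheaths.

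**The concern.** The same patient is excluded under one paragraph and counted as a failure under the next. The exclusion sentence concerns advancing the sheath, and the backup sequence begins with the randomised sheath. The event is therefore, at least in part, an outcome of the assigned device. Dropping such patients conditions on a post-assignment result of the primary objective.

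The second gap is attribution. Failure after six sheaths is a clear rule for the patient but does not compare the two devices. A patient assigned to one device may gain access with the other, with the unnamed third sheath, or at a smaller diameter. Under the patient-level rule each of these is a success for the assigned arm.

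Exclusion from the study would also take these patients' injury grades out of the comparison that sets the sample size, although up to six sheaths were tried in them. Without a stated rule, the denominator and the scoring would be chosen after the data are seen.

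**Working it through.** **The plan's own numbers.** 2 × 49 = 98 required. 117 − 98 = 19 places above that, and 19/117 = 16.2%. Against the 100 planned randomised patients, 117 − 100 = 17, and 17/117 = 14.5%. Sample Size shares this allowance among inability to gain access, rigid ureteroscopy, strictures and other causes, so 19 is an upper bound for access failures and not an estimate. At that bound, and only if all 117 had a sheath attempted, access would be 98/117 = 83.8% with failures counted and 98/98 = 100% with them excluded.

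**Effect of each scoring rule (assumed inputs).** The protocol gives no first-sheath failure or rescue rate, so these are illustrations.

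- f = probability that the randomised 12/14F sheath fails: 20% in one arm, 10% in the other.
- q = probability that a later sheath rescues a first failure: 50% to 90%, equal in both arms.

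Formulas:

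1. First-sheath success, everyone counted: 1 − f. This gives 80% against 90%, a difference of 10 points.
2. Access with any of six sheaths, everyone counted: 1 − f(1 − q). The difference is (0.20 − 0.10)(1 − q).
3. First-sheath success after excluding patients with no access: (1 − f)/(1 − f(1 − q)).
4. Access with any sheath after excluding patients with no access: 100% in both arms for every f and q, a difference of 0.

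| q | Rule 1 | Rule 2 | Rule 3 | Rule 4 |
|---|---|---|---|---|
| 50% | 10 points | 90% vs 95%: 5.0 | 88.9% vs 94.7%: 5.8 | 0 |
| 70% | 10 points | 94% vs 97%: 3.0 | 85.1% vs 92.8%: 7.7 | 0 |
| 90% | 10 points | 98% vs 99%: 1.0 | 81.6% vs 90.9%: 9.3 | 0 |

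At q = 70%, for rule 3: 0.80/(1 − 0.20 × 0.30) = 0.80/0.94 = 85.1%, and 0.90/(1 − 0.10 × 0.30) = 0.90/0.97 = 92.8%.

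Other assumed failure rates scale rule 2 in the same way. With 10% against 5%, 5 points become 2.5 to 0.5; with 30% against 10%, 20 points become 10 to 2.

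**Reading the table.** The two problems are distinct. Exclusion distorts any access rate, more when rescue is rare under first-sheath scoring (rule 3) and completely under patient-level scoring (rule 4). The any-of-six rule (rule 2) keeps everyone but hides the device difference more as rescue becomes common.

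**The case against.** Much of the case on the other side stands.

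- **Access could fail before any sheath is tried.** Background and Significance separates initial guidewire access from sheath placement, and Sample Size lists inability to gain access beside strictures, which can be found earlier. The protocol does not say when randomisation happens. A reader might infer that this item can never be a screening event; the text does not show that. The reading is weaker for the Research method exclusion, which sits in a sentence about resistance to the sheath.
- **117 enrolled against 100 randomised.** A reader might take this as evidence that randomised patients will be dropped. Ordinary screen failure before randomisation explains it equally well.
- **A large hidden difference.** Splitting 19 failures 14 to 5 over arms of 58 and 59 gives 24.1% against 8.5%, or 15.7 points. That needs all 117 to be randomised, all 19 to be access failures, and a split the protocol does not support.
- **A device difference that vanishes.** This holds only for patient-level scoring. The Data Analysis Plan speaks of device failure rates and differences between devices, which points to device-level scoring, where the difference shrinks but remains.
- **Balloon dilation.** Exclusion in one paragraph and use in another is not a flat contradiction: a surgeon can dilate for clinical reasons after study attempts have ended. The wording still leaves the study status of such a patient open.
- **Main weight on injury.** The hypothesis and sample size concern safety and injury, and access has no power statement. That limits the consequences but does not remove access from the primary objective.

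One could reconcile the paragraphs as recording a failure and then dropping the patient from the injury analysis only. No sentence says so, and the exclusion is from the study.

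**Conclusion.** The point holds. Applied as written, the Research method exclusion removes access failures after assignment. That is a rule to change, and more than a missing detail. The absence of an attribution rule for rescued patients is a separate gap.

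The size cannot be read from the documents. Under the assumed 20% against 10% first-sheath failure and 70% rescue, a 10-point difference is reported as about 7.7 points with first-sheath scoring after exclusion, 3 points with any-of-six scoring, and 0 with patient-level scoring after exclusion. These figures rest on equal rescue in both arms.

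The main harm is a misreported access rate and not a lost test. At 49 per arm, a two-sided 0.05 test of 20% against 10% has power of only 19% (Fisher) or 30% (chi-square). The point does not depend on how 49 per arm was derived. The change should be made, since the conflict is in the current text and the repair is cheap.

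**What to change.** 1. **Research method, sheath-diameter paragraph.** Delete the exclusion for inability to gain access once a randomised sheath has been attempted. Limit the balloon-dilation and semi-rigid exclusions to need found before any sheath is tried.
2. **Sample Size.** Limit inability to gain access and the rigid-ureteroscopy item to events before any sheath attempt.
3. **Data Analysis Plan, access outcome.** Analyse by randomised arm in all patients with a randomised sheath attempted, and report by arm any who were randomised but not attempted. Success means access with the randomised device. Rescue by a different device, or no access, is failure.
4. **Diameter and rescue.** Report access at 12/14F and at a smaller diameter separately, together with the six-sheath failure rate. Whether a smaller size of the assigned device counts as full success is partly a matter of preference, since the protocol permits smaller sizes on resistance; separate reporting lets readers see both. Record device, diameter and result for each attempt, which also identifies the third sheath.
5. **Injury.** Keep these patients' grades in their randomised arm where video exists, and report the number without a grade by arm. Removing the exclusion will not recover every grade: a patient stented for a staged second look may have no gradable video.

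The cost is a few sentences, one outcome definition, at most six attempt entries per patient, and slightly lower stated access rates.

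### A patient can be randomised to several sheaths in one procedure, and the plan does not say which device group that patient's ureteral injury belongs to

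*Combined protocol and SAP*

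**What the plan says.** Research method randomises each patient to one of two named sheaths. For a failed first attempt it states: "If unable to obtain access with the initial sheath the patient is randomized to, the patient will be randomized to a backup sheath". A second backup may follow, then up to three sheaths of smaller diameter in random order, so one procedure can involve six sheaths. The device used as backup is not named.

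On outcome assessment, the same section says that "ureteral wall injuries will be evaluated after removal of the UAS by a urologist" who is blinded to device and works from video. It describes no grading between attempts. Injury sites are recorded by ureteral segment, not by sheath.

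Sample Size makes this the powered outcome: "the study is powered to detect whether there is a difference between device designs to cause low (0-1) vs. high grade (2-4) ureteral injury". The Data Analysis Plan says only: "Data analysis will involve comparisons of ureteral damage between groups related to device design". It does not say whether a patient who received several sheaths is counted under the first sheath, under the last, or not at all.

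The data items listed under Research method include no record of device, diameter, order and result for each attempt.

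**The concern.** Patients who need a backup are likely to have the tighter ureters and so a higher injury risk. If they receive more than one device in the same ureter, a grade read after sheath removal reflects every sheath passed. It cannot be split between devices afterwards.

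The usual default of analysing as randomised does not resolve this, because the backup is itself assigned by randomisation and the patient has more than one assignment. The analyst is left to choose, and the choices differ. Grouping by first device keeps the randomised comparison intact. Grouping by the sheath finally in place lets an event after randomisation, first-sheath failure, decide who is in which group. The device that fails more often then loses its hardest ureters to the other and can look safer for that reason alone. The choice affects the outcome on which the trial was sized, and the plan leaves it open.

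**Working it through.** **The plan's own figures.** The documents give no first-sheath failure rate and no figure for patients exposed to more than one device, so there is nothing to reproduce on this point. The inputs that can be taken from Sample Size are:

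- reference risk: "high grade (score of 2-4) occurred in 13.3% (48/359) of patients"
- difference: "assuming a difference greater than 20% between groups is considered significant", read here as 13.3% v 33.3%
- error rates: "Using an alpha of 0.05 and beta of 0.80", with 0.80 read as power
- 49 patients per arm

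A pooled two-proportion calculation on 13.3% v 33.3% gives 69 per arm two-sided and 55 one-sided, not 49. An equivalence reading (both rates 13.3%, margin 20 points, one-sided 0.05, power 0.80) gives 2 × 0.133 × 0.867 × (1.645 + 1.282)² / 0.20² ≈ 49.4, or 50 per arm. That is a separate matter and does not affect what follows. I take 49 per arm as given.

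**Step 1. Does the grouping rule matter when the devices injure equally?** All inputs in this step are assumptions.

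- 20% of ureters in each arm are hard, with injury risk 40%. The other 80% have risk 10%. The risk depends on the ureter only, not on the device.
- Device A fails first in 20% of its arm (all its hard ureters). Device B fails first in 5% (a quarter of its hard ureters).
- The backup is the other study device and gains access.

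Grouped by first device:

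- A: 0.80 × 0.10 + 0.20 × 0.40 = 16%
- B: the same, 16%

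Grouped by final sheath:

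- A holds its 80% easy ureters plus the 5% of hard ureters that failed B: (0.80 × 0.10 + 0.05 × 0.40) / 0.85 = 0.10 / 0.85 = 11.8%
- B holds its 80% easy ureters, its remaining 15% hard ureters and the 20% of hard ureters that failed A: (0.80 × 0.10 + 0.15 × 0.40 + 0.20 × 0.40) / 1.15 = 0.22 / 1.15 = 19.1%

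The device that fails more often looks safer by 7.3 points although the injury risks are identical. If the 5% that failed B did not gain access with A and ended on some other sheath, A would show 0.08 / 0.80 = 10.0% against the same 19.1%.

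**Step 2. What does first-device grouping cost when the devices differ?** Take true risks of 13.3% (safer) and 33.3% (more injurious). Assume that every patient whose first sheath fails receives the other device, and that each device adds injury independently.

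- Risk after both devices: 1 − (1 − 0.133)(1 − 0.333) = 1 − 0.867 × 0.667 = 0.422
- Arm rate with crossover fraction c: (1 − c) × p + c × 0.422
- Power: normal approximation, pooled variance under the null, 49 per arm, two-sided 0.05

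| Crossover: safer arm / more injurious arm | Safer | More injurious | Difference (points) | Power |
|---|---|---|---|---|
| 0% / 0% | 13.3% | 33.3% | 20.0 | 65.3% |
| 5% / 5% | 14.7% | 33.7% | 19.0 | 59.5% |
| 10% / 10% | 16.2% | 34.2% | 18.0 | 53.8% |
| 20% / 20% | 19.1% | 35.1% | 16.0 | 42.8% |
| 20% / 5% | 19.1% | 33.7% | 14.7 | about 38% |
| 5% / 20% | 14.7% | 35.1% | 20.3 | about 65% |

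With equal crossover the difference is simply (1 − c) × 20 points. The last row shows no dilution when the more injurious device is also the one that fails more often.

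**The case against.** Backup sheaths serve to rescue failed access, and the trial is not a crossover design. The plan is silent on attribution and does not prescribe a wrong rule. It already intends to compare device failure rates, so part of the reporting is covered. With no failure rate given, the impact may be small: at 5% to 10% equal crossover the loss is 1 to 2 points out of 20. All of this stands, and it limits the weight of the point.

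It does not remove the gap. The exclusion in Research method for patients without access does not cover those who gain access through a backup.

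Five stronger readings are tempting, and the documents do not support them:

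- **That patients cross to the other study device.** The backup is not identified. Two devices are named, yet the sequence counts three sheaths at 12/14F. A backup could be the other device or a third one.
- **That the plan charges one device's injury to the other.** No attribution rule is stated.
- **That each patient receives only one grade.** The text describes grading after sheath removal and allows for more than one injury site. It does not say how many grades are given.
- **That first-device grouping always dilutes, and so favours the hypothesis of** "We hypothesize that the modified designs of Re-Trace and Parallel devices will demonstrate similar safety profiles". The last row of the table shows otherwise. The model also gives a sheath that failed to gain access its full injury risk, which may be too much.
- **That the sign reverses between equal devices.** A reader might set risks of 10% in uncrossed and 40% in crossed ureters, with failure of 20% v 5%, and obtain 16.0% v 11.5% by first device and 11.8% v 15.2% by final sheath. That example gives the randomised arms different ureter mixes, so 16.0% v 11.5% is a real effect of starting with A. With the same mix in both arms, first-device grouping gives 16% v 16%.

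**Conclusion.** The point holds as a gap in the analysis plan. Several sheaths can be passed in one procedure, only grading after removal is described, and no rule places such patients in a device group. For those exposed to more than one device, injury cannot be assigned to a single device. Final-sheath grouping, which the plan leaves open, would bias the powered comparison.

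The illustrated bias is a false difference of 7.3 points (11.8% v 19.1%) between devices with equal injury risk. It rests on the assumed 20% share of hard ureters, risks of 40% v 10%, and first-sheath failure of 20% v 5%. First-device grouping avoids this. Its effect on a true 20-point difference ranges from 14.7 to 20.3 points over the crossover patterns shown, assuming independent added injury. None of these rates is in the documents, so the actual size is unknown and shrinks as first-sheath failure becomes rarer. I rate this a cheap, worthwhile improvement that should be settled before results are seen.

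**What to change.** - **Data Analysis Plan:** state that the primary injury comparison groups each patient by the first randomised device, whatever sheath followed, and describe the result as the effect of starting with that device.
- **Research method:** add a record of device, diameter, order and result for each attempt.
- **Reporting:** give the number per arm exposed to more than one device. Add one sensitivity table that charges all high-grade injuries in patients exposed to both study devices first to one device and then to the other. The table informs interpretation and is not a condition for any claim.
- **Reconciliation:** Research method and Sample Size need to agree on how many sheath types are used. They also need to agree on whether patients without access are excluded, are screen failures or count as failures; all three descriptions now appear. The sponsor must decide which applies.

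The cost is a sentence in the analysis plan, a short line per attempt on the case report form, one table and the reconciled wording. The downside is that the estimate is a starting-device effect, which may be diluted when crossover is common.

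### Obtaining access is a primary objective, but access failure is not defined by device, and two of the three labels for patients without access would delete randomised failures

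*Combined protocol and SAP*

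**What the plan says.** Purpose and Objectives sets the primary objective: to "evaluate the ability for 2 different ureteral access sheaths to obtain and maintain access to the upper collecting system", together with graded ureteral injury. The Data Analysis Plan lists ability to maintain access, success rates and device failure rates among the comparisons between devices. It defines none of them and does not list obtaining access by name.

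Patients in whom access is not obtained are described in three ways:

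- **Excluded.** Research method, after allowing smaller diameters when there is resistance: "otherwise patients will be excluded from the study if unable to gain ureteral access". The same sentence then adds a second ground for exclusion: "or if ureteral balloon dilation or semi-rigid ureteroscopy is required to gain ureteral access".
- **Failure.** Research method, after the sequence of backup and smaller sheaths: "If access has not been obtained after randomization to 6 sheaths, the patient will be considered a failure". The surgeon may then stage the procedure, "proceed with ureteroscopy without a sheath, or balloon dilate".
- **Screen failure.** Sample Size requests "total enrollment of 117 patients to account for screen failures (inability to gain access, rigid ureteroscopy required, strictures, etc".

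The headcounts are "approximately 49 patients will be required per arm, for a total of approximately 98 patients" (Sample Size), 117 enrolled (Sample Size), and recruitment "to reach a total of 100 randomized subjects" (Recruitment and Consent). The time of randomisation is not stated. Two devices are randomised, but the backup sequence refers to three sheaths at 12/14F. No analysis set is given, and no rule covers patients exposed to more than one device.

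**The concern.** A comparison of how well two devices obtain access has to count failures of each device, in the arm to which the patient was randomised. The six-sheath rule does not do this. By the time it applies, the patient has been through several sheaths, and the failure belongs to no one device. The other two labels go further and take the patient out of the study.

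Two analysts following this text could therefore report different access results from the same data: one counts a first-sheath failure, another counts only six-sheath failures, and a third has no failures because those patients were excluded. Nothing in the plan prevents that choice from being made after the results are known. Removing randomised patients may also disturb the injury comparison, but only under conditions that have to be stated.

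**Working it through.** **1. The labels applied to typical patients**

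| Patient | Resistance and exclusion rule | Six-sheath rule | Sample Size wording | Device failure? |
|---|---|---|---|---|
| First sheath fails, backup succeeds | Not excluded if the backup sequence governs | Not a failure | Not covered | Not defined |
| 12/14F meets resistance, smaller sheath succeeds | Not excluded | Not a failure | Not covered | Not defined |
| Balloon dilation needed before six sheaths are tried | Excluded | Not a failure | May be a screen failure | Not defined |
| All six sheaths fail | Excluded | Failure | Screen failure | Not defined |

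The last row carries all three labels. The backup sequence starts from failure of the sheath to which the patient was first randomised, so sheath failure follows randomisation.

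**2. Headcounts**

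- Enrolled minus required: 117 - 98 = 19, and 19/117 = 16.2%.
- Enrolled minus randomised target: 117 - 100 = 17.
- Randomised target minus required: 100 - 98 = 2.

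If all 117 were randomised, at most 19 could be removed with 98 remaining. If 100 are randomised, about 2 can be lost.

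**3. What removal could hide** (arms of 58 and 59; the splits are assumptions; Fisher's exact test, two-sided)

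| Failures | Rates | Difference | p |
|---|---|---|---|
| 9 vs 10 | 9/58 = 15.5%, 10/59 = 16.9% | 1.4 points | 1.00 |
| 8 vs 11 | 8/58 = 13.8%, 11/59 = 18.6% | 4.9 points | 0.62 |
| 5 vs 14 | 5/58 = 8.6%, 14/59 = 23.7% | 15.1 points | 0.043 |

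If these patients are excluded, every row becomes 0 versus 0. With 100 randomised and 2 lost, the extreme is 0/50 versus 2/50: 4 points, p = 0.495.

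**4. How the definition changes the access gap** (illustrative)

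Assume that a sheath with failure rate f fails, in a ureter of difficulty u (standard normal), with probability Φ((√r·u - z)/√(1 - r)), where z is the standard normal quantile at 1 - f. Take r from 0.3 to 0.9, the smaller size failing at 0.2 to 1.0 times the 12/14F rate, a third device at the mean rate, and no effect of order.

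| Definition of failure | 5% vs 10% | 5% vs 20% |
|---|---|---|
| First sheath at 12/14F | 5 points | 15 points |
| First device, after downsizing | 0.4 to 3.7 | 1.5 to 11.8 |
| All six, same set in both arms | 0 | 0 |
| All six, backups omit the other arm's device | at most 0.9 | at most 3.4 |
| Failures excluded | 0 | 0 |

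With the same six sheaths in both arms, failing all of them is the same event in each arm, so the gap is 0 by construction.

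**5. The injury comparison** (illustrative)

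If a fraction f of an arm is removed, with injury risk q among those removed and p overall, the risk among those kept is (p - f·q)/(1 - f). When q = p this equals p whatever f is. A false difference therefore needs both unequal f and q different from p.

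Take p = 13.3% in both arms and r = 0.7. Let ureter difficulty explain a share s of the variance in injury liability, with s = 0 or 0.3 to 0.7:

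| Patients removed | 5% vs 10% | 5% vs 20% |
|---|---|---|
| All first-sheath failures, s = 0 | 0 | 0 |
| All first-sheath failures, s = 0.3 to 0.7 | 1.1 to 1.9 points | 2.7 to 4.5 points |
| Six-sheath failures only, same set | 0 | 0 |
| Six-sheath failures only, backups omit the other device | at most 0.25 | at most 1.0 |

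Analysis by first randomised sheath gives no false difference, but it dilutes a true one. Suppose a failed patient switches once and takes the other device's risk. If failure and injury are independent, a difference d becomes d(1 - fA - fB). For 20 points this is 20 × 0.85 = 17 (5% vs 10%) and 20 × 0.75 = 15 (5% vs 20%). With correlated failure and injury, and the more injurious device failing more, it is about 16 and 12 to 13.

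**The case against.** The strongest reply is that a screen failure ordinarily precedes randomisation, and that 117 enrolled against 100 randomised fits this. Some inability to gain access could be found at the guidewire step described in Background and Significance. This stands as far as it goes, and it is why 19 is an upper bound. The allowance also covers strictures and rigid ureteroscopy. It does not reach failure of a randomised sheath, which cannot be known beforehand, and the exclusion clause directly follows the sentence on resistance during sheath advancement.

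The six-sheath rule may be only a rule for when to stop trying. A reader might infer that it is the access endpoint, but the documents do not say so. If it is not, device failure has no definition at all.

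A reader might also infer that the injury comparison is biased, so that the device that fails more often looks safer. The documents do not support this. The backup sequence keeps first-sheath failures in the study, and nothing in the text says that difficult ureters are also more easily injured.

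Nor should much be made of balloon dilation as a point where the surgeon's choice decides the label: a six-sheath failure already meets the exclusion for inability to gain access. The two statements on dilation still need reconciling.

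Finally, injury is the only outcome for which a sample size is given. That is true, but access is still named first in the primary objective.

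**Conclusion.** The point holds and the text is wrong as written: the exclusion rule, followed literally, deletes randomised failures that a stated primary objective must count. This rests on the wording alone.

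The size cannot be determined from the documents. If failures are excluded, the access result is 0 versus 0 whatever the devices do. The number removed is at most 19 of 117 if all enrolled patients are randomised, and about 2 if 100 are. The 5 versus 14 split shows what could be hidden; it is a chosen extreme and not an expectation.

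The effect on injury is conditional. It requires exclusion at different rates by arm (the resistance and exclusion rule read alone, or early exclusions for balloon dilation or semi-rigid ureteroscopy) and also a link between difficult access and injury. If only patients failing every sheath are removed, it is near zero. Confidence is high on the inconsistency and the lost events, and low on the size of any injury bias.

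**What to change.** 1. Define the primary access endpoint as access with the first randomised sheath at 12/14F, without a change of device or diameter. Report later access (smaller diameter, backup sheath) and failure after all sheaths descriptively. Define the success, device failure and maintained-access terms in the Data Analysis Plan consistently with this.
2. Keep every randomised patient in the assigned arm for the access analysis, and score failed access as failure, never as exclusion or screen failure. State when randomisation occurs, and limit screen failure to reasons known before it.
3. Analyse injury by first randomised sheath, with a sensitivity analysis in patients exposed to one device only, labelled non-randomised. Report patients without a graded video by arm. State that the first-sheath analysis dilutes a true difference and so favours the hypothesis of similar safety.
4. Record the device, diameter and result of each attempt.
5. Reconcile the passages on two versus three sheaths, on the response to resistance, on balloon dilation as exclusion versus option after failure, and on excluded versus failure versus screen failure. The clinical sequence is for the investigators to settle.

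The cost is endpoint and analysis-set wording, one sentence on the timing of randomisation, and a few case report form fields per attempt. The reported access success rate will be lower than under the six-sheath rule, and the injury analysis will contain some patients exposed to both devices.
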